#### **Table 14.3.1.2: Treatment-emergent adverse events up to Week 12: Summary table by region**

Same table as the preceding one, but by geographical region.

Population: safety.

#### **Table 14.3.1.3: Treatment-emergent adverse events up to Week 12: Tabulation of all adverse events**

Tabulation of TEAE preferred terms per body class, per treatment group.

Population: safety.

Table to be created for the Week 12 interim analysis as well.

**Table 14.3.1.4: Treatment-emergent adverse events up to Week 12: Tabulation of all adverse events by region**

Same as previous table, but split up by geographical region.

Population: safety.

**Table 14.3.1.5: Treatment-emergent adverse events up to Week 12: Tabulation of all adverse events by gender**

Same as previous table, but split up for males and females.

Population: safety.

**Table 14.3.1.6: Treatment-emergent adverse events up to Week 12: Tabulation of all adverse events by age category**

Same as previous table, but split up for age categories:

< 45 ;

[45,65[ ;

[65,75[ ;

≥ 75 years.

Population: safety.

**Table 14.3.1.7: Treatment-emergent adverse events up to Week 12: Tabulation per intensity**

Cross-tabulation of TEAE preferred terms versus their intensity. Use the worst-case intensity per TEAE per subject. Per treatment group.

Population: safety.

Table to be created for the Week 12 interim analysis as well.

**Table 14.3.1.8: Treatment-emergent adverse events up to Week 12: Tabulation of all treatment-related events**

Tabulation of TEAE preferred terms per body class, per treatment group. Selecting only the TEAEs that were treatment-related (see section 12.1.2).

Population: safety.

Table to be created for the Week 12 interim analysis as well.

**Table 14.3.1.9: Treatment-emergent adverse events up to Week 12: Tabulation of all treatment-related events by gender****Table 14.3.1.10: Treatment-emergent adverse events up to Week 12: Tabulation of all treatment-related events by age category**

**Table 14.3.1.11: Treatment-emergent adverse events up to Week 12: Tabulation of the intensity of treatment-related events**

Cross-tabulation of TEAE preferred terms versus their intensity; per body class and per treatment group. Use the worst-case intensity per TEAE per subject, selecting only the TEAEs that were treatment-related (see section 12.1.2).

Population: safety.

Table to be created for the Week 12 interim analysis as well.

**Table 14.3.1.12: Treatment-emergent adverse events up to Week 12: Tabulation of the drug-relatedness of serious events**

Cross-tabulation of TEAE preferred terms versus their drug-relatedness; per body class and per treatment group. Selecting only the treatment-emergent serious adverse events.

Population: safety.

Table to be created for the Week 12 interim analysis as well.

**Table 14.3.1.13: Treatment-emergent adverse events up to Week 12: Tabulation of the drug-relatedness of events leading to discontinuation**

Cross-tabulation of TEAE preferred terms versus their drug-relatedness; per body class and per treatment group. Selecting only the TEAEs for which the study treatment was permanently discontinued (AE page), or for which the study was discontinued (trial termination page).

Population: safety.

Table to be created for the Week 12 interim analysis as well.

**Table 14.3.1.14: Treatment-emergent adverse events up to Week 12: Tabulation of the drug-relatedness of events leading to a temporary stop**

Cross-tabulation of TEAE preferred terms versus their drug-relatedness; per body class and per treatment group. Selecting only the TEAEs for which the study treatment was temporarily stopped (AE page).

Population: safety.

**Table 14.3.1.15: Treatment-emergent adverse events up to Week 12: Tabulation of the drug-relatedness of individual stopping rules**

Cross-tabulation of TEAE preferred terms versus their drug-relatedness; per body class and per treatment group. Selecting only the TEAEs that were flagged as “stopping criterion” in the eCRF by the investigator.

Population: safety.

### 12.1.7. Tables over the whole 24 weeks period

The same tables will be created for the full 24 weeks period of the study, using the 11 groups as specified in section 2.4.

All tables will be created for 3 analysis periods: “first 12 weeks”, “second 12 weeks”, and “full 24 weeks” as defined in section 3.2.

Population: Safety.

#### **Table 14.3.1.16: Treatment-emergent adverse events over the whole study: Summary table**

Tabulation per treatment of the number and percentage of subjects with the following:

- Subjects with at least one treatment-emergent adverse event (TEAE)
- Subjects with at least one serious TEAE
- Subjects who died (treatment-emergent)
- Subjects with at least one mild TEAE as worst intensity
- Subjects with at least one moderate TEAE as worst intensity
- Subjects with at least one severe TEAE
- Subjects with at least one TEAE that was considered treatment-related
- Subjects with at least one treatment-emergent SAE that was considered treatment-related
- Subjects with at least one TEAE for which the study treatment was temporarily stopped
- Subjects with at least one TEAE for which the study treatment was permanently stopped
- Subjects with at least one TEAE flagged as an individual stopping criterion by the investigator
- Subjects with at least one TEAE that has not resolved.

Population: safety.

#### **Table 14.3.1.17: Treatment-emergent adverse events over the whole study: Summary table by region**

(only for the “full 24 weeks”, not for the two periods separately)

#### **Table 14.3.1.18: Treatment-emergent adverse events over the whole study: Tabulation of all adverse events**

#### **Table 14.3.1.19: Treatment-emergent adverse events over the whole study: Tabulation of all adverse events by region**

(only for the “full 24 weeks”, not for the two periods separately)

#### **Table 14.3.1.20: Treatment-emergent adverse events over the whole study: Tabulation of all adverse events by gender**

(only for the “full 24 weeks”, not for the two periods separately)

**Table 14.3.1.21: Treatment-emergent adverse events over the whole study: Tabulation of all adverse events by age category**

(only for the “full 24 weeks”, not for the two periods separately)

**Table 14.3.1.22: Treatment-emergent adverse events over the whole study: Tabulation per intensity****Table 14.3.1.23: Treatment-emergent adverse events over the whole study: Tabulation of all treatment-related events****Table 14.3.1.24: Treatment-emergent adverse events over the whole study: Tabulation of all treatment-related events by gender**

(only for the “full 24 weeks”, not for the two periods separately)

**Table 14.3.1.25: Treatment-emergent adverse events over the whole study: Tabulation of all treatment-related events by age category**

(only for the “full 24 weeks”, not for the two periods separately)

**Table 14.3.1.26: Treatment-emergent adverse events over the whole study: Tabulation of the intensity of treatment-related events****Table 14.3.1.27: Treatment-emergent adverse events over the whole study: Tabulation of the drug-relatedness of serious events****Table 14.3.1.28: Treatment-emergent adverse events over the whole study: Tabulation of the drug-relatedness of events leading to discontinuation****Table 14.3.1.29: Treatment-emergent adverse events over the whole study: Tabulation of the drug-relatedness of events leading to a temporary stop****Table 14.3.1.30: Treatment-emergent adverse events over the whole study: Tabulation of the drug-relatedness of individual stopping rules****12.1.8. Listings****Listing 16.2.10.1: Treatment-emergent adverse events: Summary listing**

Listing per treatment group, per subject and per analysis period (excluding screening) of the following:

- Period start and end date
- AE preferred term (flagging serious TEAEs with an asterisk \*)
- AE start and end date
- AE onset day in study
- AE onset day in period
- AE duration
- AE intensity
- AE drug relatedness
- AE outcome
- AE action taken
- Concomitant therapy started (yes/no)
- Individual stopping criterion (yes/no)

In such a way that all information fits on one line for each AE.

Periods without an AE will be included as “no AE” records.

Population: safety.

#### **Listing 16.2.10.2: Pre-treatment adverse events: Summary listing**

Listing per treatment group and per subject of the screening analysis period of all AE details, like in the previous listing. Subjects without an AE can be omitted from this listing.

Population: safety.

#### **Listing 16.2.10.3: Adverse events: Full listing of the serious adverse events**

Listing per treatment group, per subject and per analysis period (excluding screening) of all AE details, including MedDRA coding. Only actual serious adverse events will be presented here (irrespective their treatment-emergence, so also showing any SAEs during the screening analysis period).

Population: safety.

#### **Listing 16.2.10.4: Treatment-emergent adverse events: Full listing of the events leading to discontinuation**

Same as the previous listing, but only selecting TEAEs that lead to a permanent stop of study medication, or of the study itself. This is including the “stopping rules”.

Population: safety.

#### **Listing 16.2.10.5: Treatment-emergent adverse events: Full listing of the events leading to a temporary stop**

Same as the previous listing, but only selecting TEAEs that lead to a temporary stop of study medication.

Population: safety.

**Listing 16.2.10.6: Adverse events: Coding information**

Listing of all available coding steps between AE verbatim and AE system organ class, mentioning also the subjects who had this AE.

Population: safety.

**Listing 16.2.10.7: Adverse events: Listing of subjects for whom a narrative is required**

Listing and flagging subjects who:

- Died
- Had an SAE
- Had an AE leading to study discontinuation
- Had an AE leading to a permanent stop of study drug
- Had an AE flagged as stopping criterion by the investigator in the eCRF.

Population: all screened subjects.

The clinical study report will add subject case narratives in the body of the report and/or in section 14.3.1. No standard programming is planned for this.

**12.2. LABORATORY SAFETY****12.2.1. Laboratory Units**

The statistical analysis will only present results in Standard International (SI) units. Other units will not be presented.

Lab tests with only a very low sample size ( $N < 3$  in the study total column) will not be presented in the tables, but only in the listings. Lab tests that are not part of the planned test panels according to the protocol will only be listed.

Endocrine tests will only be presented for male subjects. If any results would be available for females (not planned in the protocol), then these will be left out of the tables but still presented in the listings.

Urinalysis tests will be presented as part of the descriptive statistics and/or shift tables.

The serum CRP will not be presented in this section (is considered an efficacy parameter).

**12.2.2. Derived lab tests**

The following two “tests” will be derived from the data provided by the central lab: the ratios TC/HDL and LDL/HDL, where TC=total cholesterol, and the ratio between the CD4 and CD8 absolute counts (CD4/CD8).

Note that if the denominator is zero, the ratios will not be calculated.

The following “normal range” will be applied:

Lab test label in analysis	Normal range, males	Normal range, females
Derived TC/HDL ratio	0.0 - 5.0	0.0 - 4.5
Derived LDL/HDL ratio	0.0 - 3.5	0.0 - 3.0

No normal range is defined for the CD4/CD8 ratio.

These derived “tests” will be analyzed together with the tests provided by the lab.

### 12.2.3. Number of Significant Digits

The original results and normal limits will be rounded to present only a relevant number of digits. The Mock TLFs contains a table on the expected number of significant digits per lab test. This rounding will be done prior to any parameter derivation. Note that this table also contains the classification of lab tests into categories.

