### **8.8. ACR COMPONENT: SERUM CRP**

#### **8.8.1. Parameters**

Serum CRP (mg/L) will be analyzed as raw values, change from baseline and percent change from baseline.

Note that if for a specific visit both the regular CRP as well as the high-sensitive CRP are available, the high-sensitive CRP will be used in the analysis tables and figures. The regular CRP will then only be listed.

CRP and hsCRP values will also be categorized according to the lab’s normal ranges: normal (value  $\leq$  ULN) or high (value  $>$  ULN), where ULN = upper limit of the normal range as provided by the central lab. Note that the same ULN (8.999) will be applied to both CRP and hsCRP.

Note that CRP and hsCRP will be excluded from the lab safety analysis.

Note that the percentage change from baseline remains missing if the baseline value itself equals zero.

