### 12.2.5. Scoring of Laboratory Values

#### 12.2.5.1. Scoring according to normal ranges

All values will be compared to their matching normal ranges. The normal ranges provided by the laboratory will be used for this, as available in the database. Values will be scored as abnormally low (L), normal (N) or abnormally high (H).

A value is classified as abnormally low (L) when the value < lower limit of the normal range. A value is classified as abnormally high (H) when the value > upper limit of the normal range. Values equal to the boundaries are still considered normal (N).

An original value like “<X” where X equals the lower limit of the normal range will be classified as abnormally low (L). An original value like “>X” where X equals the upper limit of the normal range will be classified as abnormally high (H).

A normal range of “<10” will be interpreted as: lower limit = 0; upper limit = 10.

A normal range of “>10” will be interpreted as: lower limit = 10; upper limit = +INF.

Tests without normal ranges will not be scored.

Any already existing low/normal/high flags in the raw database will be ignored. The newly derived flag will be used for the analysis TLFs. Any clinical significance flags will be used in the listings.

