### 12.2.5.3. CTCAE v3.0 gradings for hematology tests

CTCAE version 3.0 classification is only for the below tests. For other tests, only the classification according to normal ranges will be done.

Lab test	Grade 0	Grade 1	Grade 2	Grade 3	Grade 4
Hemoglobin (g/L)	≥ LLN	[100,LLN[	[80,100[	[65,80[	< 65
WBC (giga/L)	≥ LLN	[3.0,LLN[	[2.0,3.0[	[1.0,2.0[	<1.0
Lymphocytes (giga/L)	≥ LLN	[0.8,LLN[	[0.5,0.8[	[0.2,0.5[	< 0.2
Neutrophils (giga/L)	≥ LLN	[1.5,LLN[	[1.0,1.5[	[0.5,1.0[	< 0.5
Platelet count (giga/L)	≥ LLN	[75,LLN[	[50,75[	[25,50[	< 25
INR and partial thromboplastin time	≤ ULN	]1.0,1.5] x ULN	]1.5,2.0] x ULN	>2.0 x ULN	(NAP)

Note:

- LLN = lower normal limit
- ULN = upper normal limit
- (NAP) = grade does not exist.

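### SAP 12.2.3 rounds laboratory results and limits before flags, grades, classes and changes are derived, which can misclassify results near a cut-off if the display digits are coarser than the laboratory's precision

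*SAP*

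**What the plan says.** SAP 12.2.3 has three parts. First, both sides of the comparison are rounded: "The original results and normal limits will be rounded to present only a relevant number of digits". Second, the digits are set in another document: "The Mock TLFs contains a table on the expected number of significant digits per lab test". Third, the order of steps is fixed: "This rounding will be done prior to any parameter derivation".

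The derivations that follow are changes and percent changes (12.2.4), low/normal/high flags (12.2.5.1), CTCAE grades (12.2.5.2 and 12.2.5.3) and ATP III classes (12.2.5.4). The lipid and CD4/CD8 ratios are defined in 12.2.2. None is exempted. Nor does the laboratory's own flag act as a check, because 12.2.5.1 says: "Any already existing low/normal/high flags in the raw database will be ignored".

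The boundary rules differ:
- In 12.2.5.1 a result equal to a limit is normal.
- In the CTCAE tables a result equal to a fixed cut-off takes the milder grade (lymphocytes Grade 2 is [0.5,0.8[; potassium-high Grade 1 is ]ULN,5.5]).
- In 12.2.5.4 a result equal to a cut-off takes the higher class (for LDL, [130,160[).

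**The concern.** Rounding for display normally comes last. Done first, it moves results that lie within half a rounding unit of a cut-off onto the cut-off, and the tie rule then decides the category. Treatment-emergent status is defined by comparing such categories with baseline (Tables 14.3.2.5, 14.3.2.8 and 14.3.2.11), so it inherits any error. Those tables, together with the CTCAE and ATP III frequency tables and the table of ±50% changes in inhibin B and testosterone, are also in the Week 12 interim package, which SAP 6.2 says is meant to support preliminary phase III dose selection.

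For flags and fixed CTCAE cut-offs the likely direction also runs against the SAP's usual caution. Missing relatedness counts as related (12.1.2), a doubtful post-baseline urinalysis result counts as abnormal (12.2.6), and QTcF is rounded up (12.3.2).

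**Working it through.** The documents give no figure to reproduce, and the digit table is not in them. The digits, ULN values and distributions below are therefore assumptions. Rounding is half-up.

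**Direction, rule by rule**

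1. *Low/normal/high flags.* If result and limit are rounded to the same digits, rounding preserves their order and can only create ties. A tie is normal, so a result can move from abnormal to normal but not back.
2. *Fixed CTCAE cut-offs on the rounding grid.* At one decimal, potassium 5.54 becomes 5.5, so Grade 2 becomes Grade 1. Lymphocytes 0.46 become 0.5, so Grade 3 becomes Grade 2. In simulations of 200,000 uniform values each for potassium, hemoglobin, neutrophils and lymphocytes, every shift was milder and none was worse.
3. *CTCAE multiples of ULN.* Here the ULN is rounded too.
   - Bilirubin 31.2, ULN 20.6: the cut-off is 1.5 × 20.6 = 30.9, so Grade 2. Rounded, 31 against 1.5 × 21 = 31.5 is Grade 1.
   - Bilirubin 30.5, ULN 20.4: the cut-off is 1.5 × 20.4 = 30.6, so Grade 1. Rounded, 31 against 1.5 × 20 = 30 is Grade 2.
4. *ATP III classes in whole mg/dL.* LDL 129.6 becomes 130 and enters the worse class; LDL 130.4 becomes 130 and stays there. Total cholesterol and triglycerides follow the same rule. For HDL the low class is the worse one, so 39.6 becoming 40 is a milder shift.
5. *Percent-change categories at -50%, whole units.*
   - 101.4 to 50.6: (50.6 - 101.4)/101.4 = -50.1%; rounded, (51 - 101)/101 = -49.5%.
   - 100.6 to 50.4: (50.4 - 100.6)/100.6 = -49.9%; rounded, (50 - 101)/101 = -50.5%.

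**Illustrative size: lymphocytes below 0.8 giga/L (Grade 2 or worse)**

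Assume log-normal counts with median m and log SD s, and F(x) = Φ(ln(x/m)/s). At one decimal, values from 0.75 up to 0.8 become 0.8. The share of true values below 0.8 that is downgraded is 1 - F(0.75)/F(0.8), and the share of all results is F(0.8) - F(0.75). At two decimals, 0.795 replaces 0.75.

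| m, s | F(0.8) | F(0.75) | Downgraded, 1 decimal | Share of all results | F(0.795) | Downgraded, 2 decimals |
|---|---|---|---|---|---|---|
| 1.6, 0.35 | 2.38% | 1.52% | 36% | 0.86% | 2.28% | 4.2% |
| 1.8, 0.35 | 1.03% | 0.62% | 40% | 0.41% | 0.98% | 4.7% |
| 1.5, 0.40 | 5.80% | 4.16% | 28% | 1.65% | 5.62% | 3.1% |

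If the digits equal the laboratory's reported precision, nothing changes. If everything is derived from unrounded values, every shift above is zero.

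**The case against.** The strongest case is that the effect may be nil. Section 12.2.3 speaks of significant digits, and at two significant digits a lymphocyte count of 0.76 stays 0.76. The documents also work with fine thresholds: 0.75 × 10⁹/L for lymphocytes in protocol 8.3.4, and 7.75 and 10.34 mmol/L for cholesterol in SAP 12.2.5.2. That makes coarse rounding of these tests doubtful. The laboratory tables are descriptive, without p-values; the same rule applies in every arm and at baseline; continuous values are tabulated as well; and rounding result and limit together keeps printed values consistent with their flags. All of this stands as a limit on size. It does not justify leaving an avoidable source of misclassification in place, and if the digits already match the laboratory's precision, early rounding of results gains nothing.

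A reader might also infer more than the text supports:

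- *That 12.2.3 contradicts 12.2.5.1*, which says "The normal ranges provided by the laboratory will be used for this, as available in the database". That sentence names the source of the ranges, and 12.2.3 says how they are prepared. The two can be read as consecutive steps.
- *That the CRP limit in SAP 8.8.1 shows the error in action* ("Note that the same ULN (8.999) will be applied to both CRP and hsCRP"). CRP and hsCRP are excluded from the laboratory safety section, and the limit there is stated unrounded.
- *That every ratio flag is affected.* SAP 12.2.2 defines no normal range for CD4/CD8, so it has no flag to misclassify.

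**Conclusion.** The point holds as a conditional one. The order of steps is explicit and no section exempts any laboratory derivation, so results near a cut-off can be misclassified wherever the mock-document digits are coarser than the laboratory's precision.

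It would be wrong to say that rounding always makes results look normal or milder. That is true for flags (equal digits), for fixed CTCAE cut-offs on the grid, and for HDL in whole mg/dL. It is reversed for the other three lipid classes in whole mg/dL, and it can go either way for multiples of ULN and percent-change categories.

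The number of trial results affected cannot be computed. The 28-40% figure is a share of a small tail, about 0.4-1.6% of all lymphocyte results, and it rests on one-decimal rounding and on medians and spreads that come from no document. The effect is probably small, and nothing in the documents shows that a dose ranking would change. Because the affected cells of the treatment-emergent and interim tables may hold few subjects, the change is still worth making.

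**What to change.** Replace the last rounding sentence of SAP 12.2.3 with: *Flags, CTCAE grades, ATP III classes, ratios, changes and percent changes are derived from the unrounded database result and the unrounded laboratory limit; rounding is applied only to printed values.*

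The cost is that one sentence and a change in program order. The downside is that a printed value may occasionally look inconsistent with its flag or grade; a table footnote saying that classification uses unrounded data covers this.

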### 12.2.4. Baseline and Change from Baseline

The baseline is defined as the last sample prior to first dosing, so should normally be from the Day -1 visit. Baseline will be determined per lab test individually. It is recognized that baseline tests may thus come from more than one lab sample and not just from the “baseline visit” sample.

The change from baseline will be calculated for all post-baseline time points as:

Change from baseline at time point t = value at time point t – baseline value.

The percentage change from baseline will be calculated for all post-baseline time points as:

Percent change from baseline at time point t = 100 x (change from baseline at time point t / baseline value).

Note that the percent change from baseline will be left missing in case the baseline value is zero.

### 12.2.5. Scoring of Laboratory Values

#### 12.2.5.1. Scoring according to normal ranges

All values will be compared to their matching normal ranges. The normal ranges provided by the laboratory will be used for this, as available in the database. Values will be scored as abnormally low (L), normal (N) or abnormally high (H).

A value is classified as abnormally low (L) when the value < lower limit of the normal range. A value is classified as abnormally high (H) when the value > upper limit of the normal range. Values equal to the boundaries are still considered normal (N).

An original value like “<X” where X equals the lower limit of the normal range will be classified as abnormally low (L). An original value like “>X” where X equals the upper limit of the normal range will be classified as abnormally high (H).

A normal range of “<10” will be interpreted as: lower limit = 0; upper limit = 10.

A normal range of “>10” will be interpreted as: lower limit = 10; upper limit = +INF.

Tests without normal ranges will not be scored.

Any already existing low/normal/high flags in the raw database will be ignored. The newly derived flag will be used for the analysis TLFs. Any clinical significance flags will be used in the listings.

